**Figure 7: Sample questions**

**Social Network Member  $\geq 50$**

 Grandpa, 80's,  
Mission district

**Questions**

Did you discuss RSV vaccine with them or their surrogate?  yes  no

If no, do you plan to discuss RSV vaccination with them in the next 3 months?  yes  no  maybe

If yes, what was the outcome of the discussion?  they already got the RSV vaccine  they scheduled an appointment  I gave them the scheduling link ..... (cont.)

the outcome of the conversation. See Figure 7 for an example of survey questions.

Implementation barriers and facilitators will be assessed as in Aim 2, with a specific focus on whether the interventions elicited responses along the intended pathways and assess subjective rating or satisfaction of interventions by participants with Likert-style questions. The endpoint survey will also include questions about vaccine confidence and specifically assess changes in trust with the BeSD core question “How much do you trust the RSV vaccine?”.

Process Metrics/CHW log: Same process measures and data collection method as described in Aim 2.

Semi-structured IDI (participants) and key stakeholders: will be assessed: We will recruit a purposive sample from each study group who completed the study procedures to understand the mechanisms by which the interventions failed or succeeded and the characteristics of who did not respond to interventions. We will use the same procedures for IDIs as discussed in Aim 2 and anticipate a sample size of N~15-25 per study group.

Focus Groups with Key stakeholders: Methods are described in Aim 2 and we will use the same focus groups with key stakeholders to assess implementation barriers for both Aims 2 and Aim 3 during the end of year 4 and quarter 1 of year 5.

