**Table 1: Primary Objectives**

Primary Objective	Endpoint(s)	Time Frame
1. Aim 1 (Developmental Aim) -Community-based survey on RSV vaccine hesitancy -Community advisory group adapts intervention components. -In depth interviews	N/A	1 year
2. Aim 2 (Motivate Trial): Determine the effectiveness of CHW counseling and text-message nudges from a CBO on RSV vaccine uptake among Latino older adults.	RSV Vaccine uptake at 60 days per California Immunization Registry (CAIR) or per medical record	60 days from time of intervention
3. Aim 3 (Activate Trial): Determine the effectiveness of CHW 'activation' counseling and text-message nudges from a CBO on activating adults to discuss RSV vaccination with older adults in their social network .	Self-reported average proportion of social network contacts $\geq 50$ years with whom participant discussed RSV vaccination at 60 days.	60 days from time of intervention

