**Study Group 1: Text message nudge**

**Study Group 2: CHW 'activation' counseling with text-message nudge**

### 7.2.2.1. Study Procedures Aim 3

**Enrollment and Randomization:** Enrollment, randomization, and intervention delivery procedures are identical to Aim 2. We will use block randomization with block sizes of 2, with stratification by sex.

**Baseline Survey:** The 25-minute questionnaire will include (1) RSV vaccine hesitancy questionnaire and demographics used in Aim 1 & 2, (2) questions on capability and confidence in recommending the vaccine, (3) Ego-centric (ego=participant) 1st degree social networks of people  $\geq 50$  years (Figure 7). Using 'name generation' techniques used widely in our prior studies, participants will be asked to list the age, gender, race/ethnicity, type of relationship, residence (district, city) and perceived RSV vaccine status of family and friends age of 50 and above. This number will be used as the denominator for the primary outcome and outcomes for each social network contact named will be assessed during the endpoint survey.

**Endpoint Survey:** Participants will complete a 60-day follow-up survey (in person preferred, but phone possible) to assess the proportion of people in their 'named' network at baseline with whom they discussed RSV vaccination. Participants will be shown the characteristics of each person (relationship, age) 'named' in their 1st degree older adult network and they will answer whether they discussed vaccination with that person, why or why not, and

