#### **9.3.1. Aim 3 Sample size considerations**

As with the secondary outcomes for Aim 2, statistical power will depend of participation in the 60-day follow-up interview. Assuming 10% attrition for the 175 participants in each arm, we will be able to detect a minimum ITT effect of 11% for any binary outcomes. For our primary outcome, assuming a standard deviation (Standard Deviation) of 0.3 for the proportion of adults contacted, with 175 participants/arm we will have 80% power (using  $\alpha=0.05$ ) to detect at least a 10% absolute increase (e.g. from 30% to 40%) in the average proportion of older adult contacts with whom RSV vaccination was discussed.

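### The sample item for the Activate primary outcome takes one yes/no for the contact or an undefined surrogate, which is wider than the endpoint in Table 1 and cannot be separated afterwards if used as shown

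*Protocol*

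**What the plan says.** Three places in the Protocol describe how a contact comes to count as discussed in the Activate trial.

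- **Section 3.1, Table 1** defines the primary endpoint: "Self-reported average proportion of social network contacts" aged 50 or over "with whom participant discussed RSV vaccination at 60 days".
- **Section 7.2.2.1, Baseline Survey and Endpoint Survey.** The contacts listed at baseline fix the denominator: "This number will be used as the denominator for the primary outcome". At 60 days each named person is shown to the participant, and "they will answer whether they discussed vaccination with that person, why or why not, and" the outcome of the conversation.
- **Figure 7, sample questions.** The item that supplies the yes or no is "Did you discuss RSV vaccine with them or their surrogate". The follow-up to a no drops the surrogate: "If no, do you plan to discuss RSV vaccination with them in the next 3 months". The text introduces the figure with "See Figure 7 for an example of survey questions", and its printed response list breaks off.

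The word surrogate occurs nowhere else in the protocol. Section 9.3.1 plans the trial on 175 per arm, a rise such as 30% to 40%, 80% power and alpha 0.05, "assuming a standard deviation (Standard Deviation) of 0.3 for the proportion of adults contacted".

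**The concern.** The endpoint definition and the survey text count a conversation held with the contact. The item also accepts a conversation held with someone else on the contact's behalf, and puts both into one answer. Because surrogate is undefined, participants and interviewers must decide for themselves who qualifies, and that person may already be on the same list of contacts.

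At stake is the meaning of the primary outcome. A proportion built from this item could be reported as contacts spoken to when it includes contacts not spoken to. Data collected in one box could not be re-scored to Table 1, so this is not something a later analysis plan can repair. The outcome is self-reported, and only the counseling arm is advised on starting these conversations and given a written action plan (section 4.4.3). Unequal use of the surrogate option is therefore possible.

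**Working it through.** **1. The planned figure.** Inputs from section 9.3.1: SD 0.3, difference 0.10, 175 per arm, alpha 0.05 (two-sided assumed). SE = 0.3 × √(2/175) = 0.0321; 0.10/0.0321 = 3.12; power = Φ(3.12 − 1.96) = 87.7%. The stated 80% is not reproduced at these inputs. With 157 per arm (10% attrition) power is 84.0%, and with 140 per arm (20% attrition) it is 79.6%. The statement is conservative, and nothing below depends on it.

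**2. What the wording allows.** Assume five named contacts and one direct conversation. By Table 1 the score is 1/5 = 0.20. If the person spoken to is also reported as surrogate for one, two or three other named contacts, the item permits 2/5 = 0.40, 3/5 = 0.60 or 4/5 = 0.80. Each contact is scored once against a fixed denominator, so the score cannot pass 1.

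**3. Equal surrogate reporting.** The protocol gives no rate, so let *s* be the assumed share of contacts not spoken to directly who are scored yes through a surrogate. The scored mean is p + (1 − p)s. With the same *s* in both arms the difference becomes (p₁ − p₀)(1 − s). Direct rates are 0.30 and 0.40, SD 0.3, 175 per arm.

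| s, both arms | Means | Difference | Power |
|---|---|---|---|
| 0 | 0.300 vs 0.400 | 0.100 | 87.7% |
| 5% | 0.335 vs 0.430 | 0.095 | 84.2% |
| 10% | 0.370 vs 0.460 | 0.090 | 80.1% |

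Both levels rise and the contrast shrinks slightly. If there is no true effect, the difference stays at zero.

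**4. Unequal surrogate reporting, no true effect.** With direct discussion at 0.30 in both arms, the false difference is 0.70 × (s₁ − s₀). For 5% vs 10% it is 0.70 × 0.05 = 0.035. Then 0.035/0.0321 = 1.09, and the two-sided rejection rate is about 19%.

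**5. A second model, with clustering inside a participant.** Assume 2 to 6 contacts (equally likely), 30% spoken to directly and independently, and, once anyone has been spoken to, each remaining contact claimed through a surrogate with probability *s*. The scored mean is 0.30 + s × the average over n = 2 to 6 of 0.7 × (1 − 0.7ⁿ⁻¹). The five terms are 0.210, 0.357, 0.460, 0.532 and 0.582, averaging 0.428.

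| s | Scored mean | SD (simulated) |
|---|---|---|
| 0 | 0.30 | 0.25 |
| 10% | 0.34 | 0.28 |
| 20% | 0.39 | 0.30 |
| 30% | 0.43 | 0.32 |

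Simulated t-tests at 158 per arm, with no true difference in direct discussion:

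| s by arm | False difference, points | Rejections |
|---|---|---|
| 10% vs 10% | 0 | about 5% |
| 5% vs 10% | 0.428 × 5 = 2.1 | about 10% |
| 10% vs 20% | 0.428 × 10 = 4.3 | about 26% |
| 10% vs 30% | 0.428 × 20 = 8.6 | about 71% |

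The simulated SDs lie around the planned 0.3. At 0.32 with 158 per arm and a 10-point effect, power is Φ(0.10/0.0360 − 1.96), about 79%, close to the planned 80%.

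**The case against.** Figure 7 is labelled as sample questions and its response list is cut off, so the full questionnaire may hold a field that identifies who was spoken to. No rule in the protocol says that a surrogate-only yes enters the numerator, and the two governing statements, Table 1 and the survey text, agree with each other. In ordinary health usage a surrogate acts for someone who cannot act alone. The example contact is a grandfather in his eighties, so the wording may be deliberate. On that reading, speaking to whoever decides for a frail relative is arguably the activation the trial wants.

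Much of this stands. It means that inflation is possible, not shown, and that loss of the defined endpoint is conditional on the item being used as printed. It does not remove the mismatch: this is the only numerator item the protocol displays, and the text sends the reader to it. If surrogate conversations are meant to count, Table 1 and section 7.2.2.1 should say so and the term needs a definition. Either intention calls for an edit.

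A reader might go further and infer that the primary proportion is inflated, that one talk with a mother will be scored for father and grandmother as well (3/3 instead of 1/3), or that the false-positive rate is 26% to 71%. The documents do not support these. The 3/3 score needs a loose reading of surrogate for two capable adults. The high error rates need a two- to threefold gap in surrogate claims between arms, for which the protocol gives no evidence. Nor does the SD argument carry weight, since the simulated values bracket the planned one.

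**Conclusion.** The concern holds as a mismatch in how the primary outcome is measured. The sample item is wider than the endpoint in Table 1 and the survey text, its key term is undefined, and one yes/no cannot separate the two kinds of conversation if it is used as shown. The scored proportion can exceed the defined one.

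The size cannot be given, because every surrogate rate used here is an assumption. Under equal reporting in the two arms the type I error stays near 5%, and the effect is a shift in level with a slightly smaller contrast (10 points to 9 at an assumed 10%). A false difference between arms arises only from unequal reporting: 5% vs 10% would add 2.1 to 3.5 points depending on the model, against a target of 10. That inequality is plausible, given what the counseling arm receives, but not established. The correction is worth making before data collection, because the information cannot be restored later.

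**What to change.** Replace the single yes/no in the per-contact item with three answers: *yes, with this person*; *yes, only with someone who makes health decisions for them*; *no*. The second answer also supplies the missing definition of a surrogate. Align Table 1, the Endpoint Survey text in section 7.2.2.1 and Figure 7 so that the primary numerator is direct discussion, as Table 1 already reads. Report direct-or-surrogate discussion as a sensitivity analysis.

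The cost is one more response option per contact and a sentence in the endpoint definition; the planned sample size need not change. The downside is that a contact reachable only through a genuine decision-maker stays in the denominator and counts as not discussed in the primary analysis. The sensitivity analysis shows how much that matters, and separate recording keeps both readings available.

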### 7.3. Schedule of Activities (Aim 2 and 3)

Aim 2 and 3 trials have a parallel structure, but differ by study population and content of interventions. However, the schedule of assessments and procedures is the same.

**Table 5: Participant Schedule of Activities**

Assessments/Procedures	Screening	Study Intervention Period				End of Study Intervention
		Visit 1 / D1 (+14)	Day 14 (Up to 14 § days after D1)	Day 28	Visit 2 / D 60 (+ 14) ^	
Study Visit / Day (Window, # Days)	Visit 0* (-60 to 0 days to D1)					
Informed Consent 1^	X					
Inclusion/Exclusion Criteria ^	X					
Randomization ^		X				
Baseline Questionnaire ^	X					
CHW counseling session and navigation ^ (Arm 2 only)			X			
Text-message				X		
Endpoint questionnaire ^					X	
Outcome Ascertainment - via medical record or California Immunization Registry						X
In-depth interviews ^†						X

 Informed consent must be obtained prior to any study-specific procedures and may be obtained prior to the screening window.

§Can take place up to 60 days after D1 if needed

^Can be done in-person or remotely (telephone or web-based platform such as Zoom)

\*Can be combined with Visit 1

†For a subset of participants only

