**Table 4: Inclusion and Exclusion Criteria**

Study	Inclusion Criteria	Exclusion Criteria
Aim 1		
RSV Vaccine Confidence Survey	(a) Adult age $\geq 18$ years (b) Speaks Spanish or English	Not able to provide informed consent
Community Advisory Groups for Adaptation of Intervention	1. Group 1: a. age $\geq 60$ years b. speaks Spanish or English c. self-identifies as Latino/a/e/x and/or indigenous group from Latin America d. lives or works in San Francisco County or Daly City and able to come to in-person meetings in San Francisco 2. Group 2: a. age 18-50 b. speaks Spanish or English c. Self-identifies as Latino/a/e/x and/or indigenous group from Latin America d. lives or works in San Francisco or Daly City and able to come to in-person meetings in San Francisco	Not able to provide informed consent  Planning on moving out of San Francisco or Daly City area in 12 months
In Depth Interviews (Aim 1)	(a) Self-identifies as Latino/a/e/x and/or indigenous group from Latin America (b) Speaks Spanish or English (c) Age $\geq 18$ years	Not able to provide informed consent
Aim 2 'Motivate Trial'	Inclusion Criteria: (a) Age $\geq 50$ years (b) Self-identify as Latino/a/x and/or indigenous groups from Latin America	(a) Intent to move outside of San Francisco in the next year

	
 
(c) Eligible for RSV vaccination per current CDC/ACIP recommendations*
 
(c) Fluent in Spanish or English
 
(d) Has not received the RSV vaccine
 
(e) Has a cell phone
 
(f) Lives or works in San Francisco or Daly City
 
(f) Able to provide informed consent
 
 
* CDC/ACIP Eligibility for RSV Vaccination:
 
 
(1) Age 75 years and older
 
(2) Age 50-74 and one of the following medical comorbidities: cardiovascular disease (e.g. coronary artery disease), lung disease (e.g. COPD, asthma), advanced chronic kidney disease, diabetes, liver disorders, neurologic or neuromuscular conditions, hematologic disorders, moderate or severe immune compromise
 
	
 
(b) Nursing home resident
 
(c) Household member participating in Aim 1 or 2
 
(d) Unable to provide consent
 

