## 6. Study Intervention and Randomizations

### 6.1. Randomization (Aim 2 & 3)

Both Aims 2 and 3 are 2 arm trials and intervention groups are described in 4.3.3 (Aim 2) and 4.4.3 (Aim 2). After enrollment participants will then be randomized to one of two study groups. Randomization will be computer generated, block randomization with random block sizes of 2, stratified by sex.

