### **6.3. Participant Discontinuation/Withdrawal from the Study**

Participants are free to withdraw from participation in the study at any time upon request.

An investigator may discontinue a participant from the study for the following reasons:

- Unacceptable adverse event(s)
- Significant study intervention non-compliance.
- Lost-to-follow up; unable to contact participant (see Section 6.4 - Lost to Follow-Up)
- Any event or medical condition or situation occurs such that continued collection of follow-up study data would not be in the best interest of the participant .
- The participant meets an exclusion criterion (either newly developed or not previously recognized) that precludes further study participation

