**Ascertainment of vaccination status:** Vaccine status will be ascertained prior to text nudge and at 60 and 90 days through the medical record or California Immunization Registry (CAIR), the medical record, or proof of vaccination from a pharmacy.

**Semi-structured IDI with participants:** In accordance with principles of Grounded Theory, we will iteratively collect and rapidly analyze interview transcript data, continuing to select

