### 9.2.1. Aim 2 Sample Size Considerations

Based on our preliminary data and a national survey, we anticipate 28% RSV vaccine uptake in our text-only arm (20% with no intervention and 8% increase with text). Assuming complete data for the primary outcome of vaccine uptake reported by CAIR, the medical record, or proof of vaccination from a pharmacy and  $\alpha=0.05$ , our sample size of N=200 per arm will conservatively

provide a minimum detectable ITT effect size of 10%. Assuming CHWs will be able to reach 90% of participants assigned to the counseling arm, our sample will be able to provide a minimum detectable ATT of 10.9%; if participants assigned to counseling are particularly hard to reach and only 80% take part in CHW counseling, we will be able to provide a minimum detectable ATT effect 12.3%.

Statistical power for secondary outcomes will depend on participation in the 60-day follow-up survey. If 10% of participants are lost to follow-up, the minimum detectable effects increase to 10.6% for ITT, 11.5% for ATT if 90% of intervention arm participants receive counseling and 12.9% for ATT if 80% of intervention arm participants receive counseling. Under a setting of high loss to follow-up, where 20% of participants in both arms are not reached for a follow-up survey, the minimum detectable effects increase to 11% for ITT, 12.2% for ATT if 90% of intervention arm participants receive counseling and 13.7% for ATT if 80% of intervention arm participants receive counseling.

Estimated treatment effects for all outcomes will be improved with statistical modeling with TMLE.

In a nested secondary pre-post analysis we will compare the proportion of people who received the RSV vaccine prior to the text-message to 30 days after the text.

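### Motivate trial: unvaccinated status may be checked up to 60 days before randomization, with no stated confirmation at D1, so people vaccinated in the gap would dilute the primary difference

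*Protocol*

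**What the plan says.** The relevant Protocol text for Aim 2 is as follows.

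- Table 4 lists "Has not received the RSV vaccine" as an inclusion criterion.
- Table 5 marks the inclusion/exclusion row only under screening, whose column reads "Visit 0* (-60 to 0 days to D1", and the randomization row only under Visit 1/D1. The asterisk note on Visit 0 says "Can be combined with Visit 1", which permits a same-day check but does not require it.
- Section 6.1 says "After enrollment participants will then be randomized to one of two study groups" and mentions no repeat eligibility check.
- Section 7.2.1.1 says "Vaccine status will be ascertained prior to text nudge and at 60 and 90 days". No day is given for the first of these look-ups. Table 5 puts the text itself at Day 28.
- Section 6.3 allows discontinuation when "The participant meets an exclusion criterion (either newly developed or not previously recognized) that precludes further study participation".
- Section 9.2 analyses the primary outcome by intention to treat over all participants, with the Fisher exact test.
- Section 9.2.1 says "we anticipate 28% RSV vaccine uptake in our text-only arm (20% with no intervention and 8% increase with text", citing preliminary data and a national survey. The time span of those sources is not given.

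**The concern.** Unvaccinated status is the one eligibility criterion that the primary outcome itself overturns, and it can go out of date while a participant waits for randomization. Section 1.1 describes a single-dose vaccine, so a person vaccinated between Visit 0 and D1 no longer meets the criterion and can no longer become newly vaccinated. That person still enters the intention-to-treat set as a fixed outcome: an event if status at 60 days is what counts, a non-event if only doses after D1 count. The Protocol does not say which. Either way the person adds nothing to the difference between arms. What is at stake is power, and the randomization of people who do not meet the protocol's own criterion.

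**Working it through.** **Inputs.** From section 9.2.1: 200 per arm, 28% uptake in the text-only arm, a 10-point minimum detectable intention-to-treat effect (so 28% vs 38%), α = 0.05, complete primary-outcome data, and 20% uptake with no intervention. Sidedness and power are not stated for Aim 2. I take two-sided α, and 80% power as in section 9.3.1. The gap of 0 to 60 days is from Table 5.

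**The plan's own figure first.** Power = Φ[(d√n − 1.96·√(2p̄q̄)) / √(p₁q₁ + p₂q₂)]. With d = 0.10, n = 200 and p̄ = 0.33: (1.414 − 1.96 × 0.665) / 0.661 = 0.168, so power is 56.7% (52.7% for the exact Fisher test). The difference detectable at 80% power is 13.3 points two-sided, or 11.7 one-sided. The stated 10 points is not reproduced. That is a separate sample-size problem; here it only explains why the starting power is low.

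**Share vaccinated in the gap.** Suppose the 20% is a 60-day rate with constant hazard (an assumption). Then f(t) = 1 − 0.8^(t/60):

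- 7 days: 2.6%
- 14 days: 5.1%
- 30 days: 10.6%
- 60 days: 20%
- Gaps spread evenly over 0 to 60 days: 1 − 0.2/(−ln 0.8) = 1 − 0.2/0.223 = 10.4%
- Visits combined: 0%

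If the 20% instead accrued over 6 to 12 months (also an assumption), the share at the maximum gap is 1 − 0.8^(60/180) = 7.2% down to 1 − 0.8^(60/365) = 3.6%.

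**Dilution.** If doses before D1 count as events, each arm's rate is f + (1−f)p. If they do not, it is (1−f)p. In both cases the difference is (1−f) × 10 points.

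| f | Difference | Rates and power, counted as events | Rates and power, not counted |
|---|---|---|---|
| 0 | 10.0 | 28.0% vs 38.0%: 57% | 28.0% vs 38.0%: 57% |
| 5% | 9.5 | 31.6% vs 41.1%: 51% | 26.6% vs 36.1%: 54% |
| 10% | 9.0 | 35.2% vs 44.2%: 45% | 25.2% vs 34.2%: 50% |
| 20% | 8.0 | 42.4% vs 50.4%: 36% | 22.4% vs 30.4%: 44% |

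**Effect needed among the unvaccinated for 80% power.** It rises from 13.3 points to 13.8–14.3 at f = 5%, 14.4–15.3 at 10% and 15.8–17.5 at 20%.

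**Removing these people afterwards instead.** Numbers fall to 190, 180 and 160 per arm, with power 55%, 52% and 48%. Screening them out before randomization and enrolling to 200 per arm keeps 57%.

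**The case against.** The strongest reply is that the gap may be short or absent. Visit 0 may be combined with Visit 1, and if sites routinely do this the problem disappears. A reader might infer from the 60-day window that a fifth of participants will enter already vaccinated. The documents do not support that: it needs everyone screened at day −60 and the 20% read as a 60-day rate. Section 9.2.1 does use the 20% to build a 60-day outcome, but does not say over what period it arose. Section 1.1 gives 24% cumulative uptake in adults over 60 by May 2024, after introduction in 2023. Assuming 10 to 12 months, that is 1 − 0.76^(60/300) = 5.3% to 1 − 0.76^(60/365) = 4.4% per 60 days.

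A reader might also infer that status is never checked again. That is too broad: section 7.2.1.1 plans a look-up before the text, and its wording would even admit one at D1. But nothing requires it before randomization, and a look-up afterwards can identify these people without keeping them out of an analysis over all participants. The discontinuation clause does not fill the gap. It concerns exclusion criteria, prior vaccination is a failed inclusion criterion, and discontinuation does not take anyone out of intention to treat.

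Finally, vaccination dates will be available, since time to vaccination is a secondary outcome, and a coding rule for early doses may stand in an analysis plan that is not shown. That is fair, but such a rule only chooses between the last two columns of the table. It does not restore the lost difference.

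**Conclusion.** The point holds as a limited, inexpensive improvement. When Visit 0 and Visit 1 are separate, the Protocol states no confirmation of unvaccinated status before randomization, and anyone vaccinated in the gap shrinks the intention-to-treat difference by (1−f). A plausible range for f is near 0 to about 10%, with 20% as a ceiling. That turns a 10-point effect into 9.0 to 10 points, or 8.0 at the ceiling. Two-sided power moves from 57% to 51–54% at f = 5%, 45–50% at 10% and 36–44% at 20%. These figures rest on a constant hazard, on the reading of the 20%, and on the distribution of gaps, which the Protocol does not give.

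Two stronger inferences fail. The comparison between arms is not biased, because vaccination before randomization cannot depend on the arm. Nor should the low power figures be laid wholly to this window: 57% is the starting point before any dilution.

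**What to change.** 1. In Table 5 and section 6.1, require that when Visit 0 and Visit 1 fall on different days, unvaccinated status is confirmed by CAIR or medical record on D1 before randomization, and that anyone found vaccinated is not randomized.
2. In the primary endpoint definition, count only doses dated after randomization as events.
3. If doses found later to predate randomization are to lead to removal from an analysis set, limit this to dates from a registry or record query run identically in both arms, and report the full intention-to-treat result alongside. Pharmacy proof or self-report should not trigger removal: Arm 2 has extra contact with community health workers, so early doses could surface more often there, and the exclusion would no longer be neutral between arms.

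The cost is one query per participant with separate visits, using access the study already plans, and a few late screen failures to replace.
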